a. Randomized trial subjects: Adult MGH employees (21 years or older) who use any of the MGH cafes and cafeterias four or more times a week, are willing to receive email messages through their Partners email, and pay for all cafeteria food and beverage purchases with the Platinum Plate or ID card will be eligible to enroll in the trial. For those employees who do not regularly access their Partners email through their normal work routine, study staff will provide assistance in setting up a channel for easy access such as through an encrypted smartphone, laptop, or personal desktop computer. Employees who are actively trying to gain weight, know that they will be leaving their employment at MGH within the next 12 months or will be absent from MGH for more than a month in the next year (i.e. retirement, end of training, relocation), who are currently pregnant or planning a pregnancy within the next 12 months, who have had weight loss surgery within the past 12 months or are planning a weight loss surgery during the next 12 months, who have ever had or been diagnosed with an eating disorder, or who are currently enrolled in the Be Fit 10-week employee wellness program will not be eligible to enroll in this study. Employees who enroll in the study will not be eligible to participate in Be Fit during the two year study. In addition, cashiers at the cafes and cafeterias involved in this study (Eat Street, Coffee Central, Blossom, Tea Leaves, Riverside, Coffee South, [name]) will not be eligible to enroll as their job requires them to ring up purchases, which will serve as data in our study.

b. Employee network: For Aim 3, all MGH employees who use a platinum plate card for cafeteria purchases during the 1-year intervention period will be included in analyses for Aim 3.

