B. Procedures for obtaining informed consent: The study coordinator and the PI will be responsible for obtaining informed consent. Informed consent will explain that subjects will be randomized to either an intervention or a control group, and therefore there will be a 50% chance of receiving the intervention. Subjects will be informed that participation in the study will take place over a 2 year period. Subjects will be told that if they are assigned to

the intervention they will receive a monthly letter at their home and weekly emails and that information collected from their cafeteria food purchases and from their baseline surveys and measurements will be used to create personalized messages. Subjects will be informed that if assigned to the intervention they will be eligible to earn small incentives to increase their healthy cafeteria purchases, but if they are assigned to control, they will not be eligible for the incentives. The consent form will outline the schedule of assessments and surveys for all study participants that take place at baseline, 6 months, 1 year, and 2 year follow-up. Subject remuneration for completing outcomes assessments will be described in detail, and these include \$100 to be paid to each subject for completing each assessment at baseline, 1 year, and 2 years (survey, physical assessments, fasting blood, and two dietary recalls) and \$25 for completing two 24-hour dietary recalls at 6 months. The consent form will describe that the subjects in both the control and the intervention groups will receive 10% off all purchases made with the cafeteria Platinum Plate or ID card and that all their cafeteria purchase data will be collected by the research team. The consent form will explain that in order to receive the 10% discount in the cafeterias, subjects will need to have a study sticker placed on the back of their hospital ID or on the Platinum Plate card that will be shown to the cashier at the time that they are paying for their purchases. This discount is only to be used for cafeteria purchases made for subjects' own consumption. Periodically study staff will review purchasing history and if it appears that subjects are using this discount to pay for their co-workers' cafeteria purchases on a regular basis, study staff will contact the subject with the possibility of discontinuing the 10% discount.

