Survey: All subjects will complete a baseline survey electronically (or a paper version if the subject does not have computer access) to provide subject's and subject's immediate family's medical history, subject's medications, smoking history, physical activity level, eating habits and behaviors, perceived stress, use of the Internet, demographic background, and body weight goal for the year (i.e. maintain current weight, lose weight). The same survey will be repeated at one year and 2 years with static questions (i.e. demographics) removed in the follow-up surveys.

Physical assessments and fasting blood: Assessments will be performed by research nurses in the Clinical Research Center (CRC) at MGH. The CRC is centrally located in the main hospital building and will be convenient for most employees. If an employee is unable to visit the CRC for an assessment due to job responsibilities or unforeseen circumstances, a research nurse will be able to meet them at a convenient location to complete the assessment. The employee will be asked to fast for 12 hours prior to the assessment. Assessments will include measurement of the subject's weight, height, waist and hip circumference, and blood pressure. Physical activity will be measured with the International Physical Activity Questionnaire.⁹⁵ Blood measurements will include a lipid panel (total cholesterol, LDL, HDL, and triglycerides), glucose, and HbA1c. Resting energy expenditure will be measured using the VMAX Encore 29 metabolic cart, Viasys Healthcare, Carefusion, San Diego, CA, using best practice methods.⁹⁶ All measurements will be repeated at 1-year and 2-year follow-up, with the exception of the resting energy expenditure assessment which will only be performed at the baseline visit.

b. Outcomes: Primary outcomes will be change in weight at 1 year and 2 years follow-up compared to baseline. Secondary outcomes will be change in waist circumference and body mass index.

c. Analysis: We will compare the change in weight between intervention and control groups at the end of 1-year and 2-year follow-up using two-sample t-tests. We will also use repeated measures analyses to combine data from both time points using mixed effects models. A time-treatment interaction term will be included in the models. We will evaluate 1) the overall average treatment effect across 1 year and 2 years and 2) the treatment group

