difference in the change from baseline to 1 year and from baseline to 2 years. The known predictors of weight change will also be included in the mixed effects models to improve the precision of parameter estimates.

d. Power calculation: A total of 670 subjects will be recruited. From a previous study,⁹⁰ we expect a <10% attrition rate and we do not expect the attrition rate to be different between the two study groups since change of employment was the main reason for loss-to-follow-up in our prior study. The final sample size for analysis will be 540, or approximately 270 per group. Using the data from our prior worksite exercise and nutrition studies, we estimate the standard deviation in weight change at 1 year is about 5 pounds. With 270 subjects per arm, the study will have 93% power to detect a mean difference as small as 1.5 lbs between the two study arms with a two-sided significance level of 0.05.

2. Hypothesis 1.2: Employees in the intervention group will have lower cholesterol, blood pressure, and hemoglobin A1c than the control group at 1 year and 2-year follow-up.

a. Outcomes: Outcomes will be change in total cholesterol, blood pressure, and HbA1c at 1 year and 2 years follow-up compared to baseline. Secondary outcomes will be change in waist circumference, LDL cholesterol, triglycerides, and glucose at 1 year and 2 years compared to baseline.

b. Analysis: We will compare the changes in the primary and secondary outcomes between intervention and control groups at the end of 1-year and 2-year follow-up using two-sample t-tests or Wilcoxon rank sum tests, whichever more appropriate. We will also use repeated measures analyses to combine data from both time points using mixed effects models. A time-treatment interaction term will be included in the models. We will evaluate 1) the overall average treatment effect across 1 year and 2 years and 2) the treatment group difference in the change from baseline to 1 year and from baseline to 2 years. The known predictors of outcomes will also be included in the mixed effects models to improve the precision of parameter estimates.

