Primary analyses will be performed on an intent-to-treat basis that includes all randomized participants. Missing data could occur in several scenarios: (1) Loss to follow-up due to leaving employment, which is expected to have occurred at random in both groups and to be unrelated to the study outcomes; (2) Failure to attend a follow-up appointment or a visit to obtain a weight measurement; and (3) Censoring due to pregnancy. For participants who became pregnant during the intervention year, their follow-up values on all outcomes will be considered missing. We will impute missing data using multiple imputation and employing all available outcomes assessments and all prior data including baseline data, HEI conducted measured at 6 months, and all purchasing data prior to 2-year follow-up. We will conduct two sensitivity analyses: (1) including only participants who completed follow-up assessment at 1 year and (2) including only participants who remained employed at the hospital during the one-year intervention. If sensitivity analyses yield substantively different results, we will conduct exploratory analyses to assess reasons for the difference.

Hypothesis 1.1: The primary outcome is change in weight (kg) at the end of one year. Change in weight at the end of two years is a secondary outcome. Other secondary outcomes include *percent* body weight lost and gained less than 1 lb. We will compare the change in weight between intervention and control groups using a difference-in-

differences approach. To improve the precision of the effect estimate, we will use a linear/logistic regression analysis including age, sex, race, ethnicity, education, job type, and physical activity in the model.

We will use a repeated measures approach to combine data from 1-year and 2-year weight outcomes. A mixed effect model with a random effect for subject and a time treatment interaction will be used to examine the intervention effect at each time point and over the entire period.

Hypothesis 1.2: We will compare the changes in each of the cardiometabolic risk factors (waist circumference, systolic and diastolic blood pressure, fasting glucose, HbA1c, triglycerides, LDL and HDL cholesterol, total cholesterol) between intervention and control groups at the end of 1-year and 2-year follow-up using a difference-in-differences approach. The analysis strategy will be identical to the one used for the primary outcome in Hypothesis 1.1.

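### The weight-loss surgery criterion looks ahead only 12 months although weight is analysed at 2 years, so surgery already planned for months 13 to 24 can enter the 2-year comparison

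*Combined protocol and SAP*

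**What the plan says.** **Eligibility.** Protocol section III.B.1.a excludes employees "who have had weight loss surgery within the past 12 months or are planning a weight loss surgery during the next 12 months". The same paragraph says of a competing worksite programme: "Employees who enroll in the study will not be eligible to participate in Be Fit during the two year study".

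**Duration and outcomes.** On consent, section IV.B says: "Subjects will be informed that participation in the study will take place over a 2 year period". Section VI.A.1.b says: "Primary outcomes will be change in weight at 1 year and 2 years follow-up compared to baseline". The Analysis Plan of June 2019, under Hypothesis 1.1, makes 1-year weight change the primary outcome and 2-year weight change secondary. It also combines both time points in a mixed model with a time-by-treatment interaction.

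**Power.** The power statement in section VI.A.1.d is "With 270 subjects per arm, the study will have 93% power to detect a mean difference as small as 1.5 lbs", for a two-sided test at the 0.05 level. On variability the same section says "we estimate the standard deviation in weight change at 1 year is about 5 pounds". No SD or power is stated for 2-year weight.

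**Events after enrolment.** The Analysis Plan is intent-to-treat on all randomized participants. The one clinical event for which it sets outcome values aside is pregnancy: "For participants who became pregnant during the intervention year, their follow-up values on all outcomes will be considered missing". It has no rule for weight-loss surgery. The two sensitivity analyses are restricted to 1-year completers and to those who stayed employed during the intervention year.

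**The concern.** The look-ahead ends where the 1-year assessment falls, but weight is measured and compared a year beyond that. Someone who tells the coordinator that an operation is arranged for month 14 passes the screen. That participant's 2-year weight then reflects the operation, and nothing in the Analysis Plan treats it differently from any other weight.

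This matters because the trial works on a small scale: a target difference of 1.5 lb against an SD of 5 lb. A single large surgical loss can move an arm's mean by a visible fraction of the target, in a direction set by chance allocation, or it can widen the interval. The planned covariates (age, sex, race, ethnicity, education, job type, physical activity) would not be expected to absorb an outlier of this kind. A surgical case who attends the 1-year visit and stays employed remains in both planned sensitivity analyses.

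**Working it through.** **Which endpoint the window reaches**

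| | Months 0 to 12 | Months 13 to 24 |
|---|---|---|
| Surgery planned at enrolment | excluded | eligible |
| Surgery decided on after enrolment | not caught by any question about plans | not caught |
| Weight outcome first affected | 1 year | 2 years |
| SD and power in the documents | 5 lb, 93% | none |

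The gap in the criterion is therefore confined to 2-year weight and to the mixed model that uses it.

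**Reproducing the stated power.** Inputs from section VI.A.1.d: n = 270 per arm, difference 1.5 lb, SD 5 lb, two-sided 0.05.

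- SE = 5 × √(2/270) = 0.430 lb
- Power = Φ(1.5/0.430 − 1.96) = Φ(1.526) = 93.6% (93.6% also with the noncentral t)

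This agrees with the stated 93%.

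**Illustration for 2-year weight.** Four inputs are assumptions that the documents do not supply: the 5 lb SD still holds at 2 years; 270 per arm are analysed then; surgery adds a loss L of 60 lb, range 30 to 90 lb; and operations occur in the numbers given below.

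*(a) One operation, in one arm only.* That arm's mean shifts by L/270.

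- L = 60: 0.22 lb, 15% of 1.5 lb
- L = 30: 0.11 lb, 7%
- L = 90: 0.33 lb, 22%

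*(b) Exactly one operation in each arm, equal loss.* The two mean shifts cancel, so the true sampling error of the difference stays at 0.430 lb. The estimated SD still rises, to SD′ = √(25 + (1/270)(269/270)L²). Power = Φ[(1.5 − 1.96 × SD′ × √(2/270)) / 0.430].

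*(c) Operations at random, averaging 1 in 270.* The variance is the same, but chance imbalance between arms now adds to the true error too. Power = Φ[1.5/(SD′ × √(2/270)) − 1.96].

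| L (lb) | SD′ (lb) | (b) one in each arm | (c) random, 1 in 270 |
|---|---|---|---|
| 0 | 5.00 | 93.6% | 93.6% |
| 30 | 5.32 | 92% | 90–91% |
| 60 | 6.19 | 85% | 80% |
| 90 | 7.41 | 72% | 65–67% |

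For L = 60 in (b): SD′ × √(2/270) = 0.533; (1.5 − 1.96 × 0.533)/0.430 = 1.06; Φ = 85.5%. In (c): 1.5/0.533 − 1.96 = 0.86; Φ = 80.4%. Simulated two-sample t-tests agree: about 85% for (b) and 80% for (c). At L = 90 in (c) the formula gives 65% and simulation about 67%, hence the range in the table.

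**The case against.** **The 12-month horizon may be deliberate.** Every look-ahead question in section III.B.1.a uses about a year: leaving employment, long absence, pregnancy and surgery. That matches the intervention year and the 1-year primary outcome. The two-year Be Fit rule is a condition on enrolled participants, not a question about plans, so the differing horizons are not a contradiction. This stands. It explains the choice, but it does not protect the 2-year outcome.

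**A reader might infer that one operation per arm cuts the stated 93% power to about 80%.** The documents do not support that. The 93% belongs to 1-year weight, and the present screen already covers surgery planned up to that point; an operation in month 14 cannot alter a 1-year weight. Nor is 80% the result for exactly one equal loss in each arm, which gives about 85% at 60 lb. The 80% figure needs operations occurring at random at an average rate of 1 in 270.

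**A reader might also infer that post-surgical weights must be set to missing in the main analysis, as for pregnancy.** That is a choice of estimand. Under intent-to-treat, keeping observed weights after a post-randomization event is a standard treatment-policy reading. Participants may hold weight-loss goals, so surgery could itself be related to assignment. The pregnancy rule is also limited to the intervention year. The objection holds for the main analysis; it does not argue against a sensitivity analysis.

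**The deciding inputs are outside the documents.** This is true of the operation rate and the size of the loss. The prior-study SD of 5 lb may also already include rare cases of this kind.

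**Conclusion.** The point holds for 2-year weight. The criterion admits people who disclose surgery planned for months 13 to 24, and their post-surgical weights enter the 2-year comparison and the mixed model as observed. The 1-year power statement is not affected by this window.

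The size cannot be derived from the documents. If the 5 lb SD and 270 per arm carry over to year 2 and the surgical loss is 60 lb (30 to 90 lb), the effect depends on how the operations fall:

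- one case in one arm shifts that arm's mean by about 15% of the 1.5 lb target (7% to 22%);
- exactly one in each arm takes power from about 94% to about 85% (92% to 72%);
- random operations averaging 1 in 270 take it to about 80% (90% to 65–67%).

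With no such operations the effect is nil. Separately, surgery not planned at enrolment could occur in either year. A planning question cannot prevent that, and no planned analysis shows how far it influences the results. This is a modest design gap with a cheap remedy, and it gives no ground for doubting the primary 1-year comparison.

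**What to change.** 1. **Criterion (section III.B.1.a).** Change the forward-looking part of the surgery exclusion from 12 to 24 months, so that it spans the follow-up over which weight is analysed. This changes one number and loses a few candidates who plan surgery in the second year. If enrolment has already closed, only item 2 remains available.

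2. **Analysis Plan.** Keep the intent-to-treat analysis with observed weights as the main analysis. Add one sensitivity analysis that sets weight and cardiometabolic values measured after weight-loss surgery, in either year, to missing and imputes them with the multiple imputation already planned. The cost is one or two sentences and one further model run, and the date of any such operation must be recorded at follow-up. Fixing this before analysis avoids deciding how to treat an outlier after seeing it.

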As per the Partners IRB protocol, subjects and the person obtaining consent will sign two copies of the informed consent. One copy will remain on file with the Principal Investigator (PI), and the other copy will be given to the study participant. Information about contacting the study PI will be included on the consent form, and it will be explained that the subject can withdraw from the study at any time.

C. Treatment assignment and randomization: After providing informed consent and completing the baseline survey and CRC visit, the subject will be assigned to one of the two treatment conditions (intervention group or control group), stratified by weight-loss vs. weight-maintenance goals, using a computer-generated randomization scheme created by the study statistician. Study coordinators and subjects will be blinded to treatment assignment until the baseline assessment is completed.

V. Study Procedures:

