Hypothesis 2.1: We will compare the healthfulness of food and beverages purchased at work between the intervention and control groups. Outcomes will include the average proportion of items purchased that are labeled green and labeled red, the average Healthy Purchasing Score, and the average number of calories of purchased foods during each one-year period (intervention period and follow-up period) compared to the baseline period (one year prior to enrollment). The analysis strategy will be identical to the one used for the primary outcome in Hypothesis 1.1.

Secondary analyses will explore the trend of these outcomes. We will explore whether the intervention effects diminish over time using a repeated measures approach. The mixed effect models will include a random effect for subject and a time treatment interaction fixed effect to determine whether the intervention effects differ among quarters or whether any trend exists.

Hypothesis 2.2: We will compare the change in dietary intake (via the Healthy Eating Index) of the intervention and control groups during the intervention year using 3 follow-up time points: 6 months, 1 year, and 2 years. We will utilize a mixed effects model that includes a random effect for subject and a time treatment interaction fixed effect to examine the intervention effect at the two time points separately. We will also add age, sex, race, ethnicity, education, and job type to the model to increase the precision of effect estimate.

VII. Risks and Discomforts

For all subjects, including the larger population of employees included in Aim 3 of the project, procedures to protect the privacy and to maintain confidentiality of data include the following: 1) Access to subject information will be protected by a Partners secure server. External access to such information is blocked by secure external firewalls. 2) Subjects will be assigned a unique study identification number. All data and the key linking the study identification number to the subject's information will be maintained on a Partners secure server that is password protected. 3) Identifiable study data will not be analyzed or published in any fashion that provides the ability to identify subjects.

[name] will screen all blood test results and will contact subjects individually to inform them of any critical results and to refer them for appropriate medical follow-up.

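### Randomisation is stratified by weight goal, but no outcome model in the Analysis Plan names that stratum. Adding it costs about one degree of freedom, for a small gain in the linear weight analysis.

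*Combined protocol and SAP*

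**What the plan says.** **Design.** Section IV.C (Treatment assignment and randomization) says that assignment is "stratified by weight-loss vs. weight-maintenance goals, using a computer-generated randomization scheme". This is the only stratification factor. Section VI.A.1.a (Survey) lists, among the items every subject completes at baseline, "body weight goal for the year (i.e. maintain current weight, lose weight".

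**Analysis Plan (June 17, 2019).**
- Hypothesis 1.1 specifies a "linear/logistic regression analysis including age, sex, race, ethnicity, education, job type, and physical activity in the model". The stated purpose is precision. Hypotheses 1.2 and 2.1 adopt the same strategy.
- For the two follow-up visits together: "A mixed effect model with a random effect for subject and a time treatment interaction will be used to examine the intervention effect". No covariates are listed.
- Hypothesis 2.2 has its own list: "We will also add age, sex, race, ethnicity, education, and job type to the model to increase the precision of effect estimate".
- Missing data are imputed "employing all available outcomes assessments and all prior data including baseline data". Goal is not named.

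**Protocol, section VI.A.1.c.** The mixed models carry an open-ended clause: "The known predictors of weight change will also be included in the mixed effects models to improve the precision of parameter estimates".

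The documents do not say whether randomisation was blocked within strata, how many subjects chose each goal, or how weight change differs between the two groups.

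**The concern.** The plan adjusts for seven baseline variables in order to gain precision, yet leaves out the one variable the investigators thought important enough to stratify on. That variable also bears plausibly on the primary outcome: people who set out to lose weight may well change differently from people who set out to hold it.

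What is at stake depends on how the strata were randomised.
- **Blocked within strata.** The arms are balanced on goal by design. A model without goal counts between-stratum variation as noise, so its standard error is too large and its test conservative. Adding goal corrects the reported standard error but does not change the true spread of the estimate.
- **Not blocked.** Chance imbalance in goal remains, and adding goal is a real gain in precision.

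There is a second, practical risk. The documents contain more than one goal: the baseline survey item, the calorie goal that intervention subjects choose (V.A.2.i), and a goal that can be changed at any time during the intervention (V.A.2.vi). If goal is added later without definition, an analyst could pick a version that exists in one arm only or that was set after randomisation.

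**Working it through.** **Inputs from section VI.A.1.d:** SD of one-year weight change 5 lb; target difference 1.5 lb; two-sided 0.05; 540 analysed, about 270 per arm. The same paragraph gives 670 recruited with under 10% attrition, which would leave about 670 × 0.9 = 603, so both sizes are carried.

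**Inputs assumed:** share *p* in one stratum; gap *d* in mean weight change between strata, not explained by the listed covariates.

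**The plan's own figure.** SE = 5 × √(4/540) = 0.430 lb. Power = Φ(1.5/0.430 − 1.96) = 93.6%, which agrees with the stated 93%. The 95% half-width is 1.96 × 0.430 = 0.843 lb (0.383 kg). At 603: SE 0.407 lb, half-width 0.798 lb, power 95.8%.

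**Effect of adding goal.** The stratum explains R² = p(1−p)d²/25 of the variance, and the interval narrows by 1 − √(1−R²), whatever the sample size. Example, 60/40 and 2 lb: R² = 0.24 × 4/25 = 0.0384; narrowing = 1 − √0.9616 = 1.9%.

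| Gap (lb) | 50/50 | 60/40 | 80/20 |
|---|---|---|---|
| 0 | 0% | 0% | 0% |
| 1 | 0.5% | 0.5% | 0.3% |
| 2 | 2.0% | 1.9% | 1.3% |
| 3 | 4.6% | 4.4% | 2.9% |
| 4 | 8.4% | 8.0% | 5.3% |

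The 4 lb row is an outer bound: 4/1.5 = 2.7 times the target effect. If the other covariates already explain 10 to 20% of the variance and the gap persists after them, the 50/50 figures become 0.56 to 0.63% at 1 lb and 2.25 to 2.53% at 2 lb. The lost degree of freedom (538 to 537) widens the critical value by about 0.0004%.

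**In absolute terms (60/40, before imputation variance).** At 540 the half-width goes from 0.843 lb to 0.839 lb (1 lb gap) or 0.827 lb (2 lb gap), and adjusted power is 93.9% or 94.5%. At 603 the half-width goes from 0.798 lb to 0.794 or 0.783 lb, and adjusted power is 95.9% or 96.4%.

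**Blocked strata.** The unadjusted test already benefits from balance, so the fair comparator is Φ((1.5 − 1.96 × 0.430)/SE_adj). At 60/40 and 540 this is 93.7% at 1 lb and 94.0% at 2 lb, so adjustment adds only about 0.1 and 0.5 points.

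**Simulation** (540 subjects, 60/40, total SD 5 lb, effect 1.5 lb, assumed control mean change +1 lb; 4,000 trials for power and 6,000 for type I error per setting). Each cell gives the model without goal, then with goal.

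| Linear model | Empirical SE (lb) | Model SE (lb) | Type I error | Power |
|---|---|---|---|---|
| Blocked, 2 lb | 0.427 / 0.427 | 0.430 / 0.422 | 4.7 / 5.1% | 93.5 / 93.8% |
| Blocked, 4 lb | 0.393 / 0.393 | 0.430 / 0.396 | 3.2 / 4.8% | 95.0 / 96.3% |
| Unblocked, 4 lb | 0.426 / 0.392 | 0.430 / 0.396 | 5.0 / 4.8% | 94.0 / 96.7% |

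With blocking, only the reported SE moves. Without it, the real spread falls.

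**Binary secondary outcome** ("body weight lost and gained less than 1 lb"). The interval does not narrow here, because adjustment also changes the odds ratio being estimated. With blocked strata and a 4 lb gap, the mean log odds ratio goes from 0.480 to 0.541, its SE from 0.175 to 0.187, and power from 80.6 to 83.0%. At 2 lb the SE goes from 0.175 to 0.178 and power from 78.8 to 79.0%, a difference within simulation error.

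**The case against.** The strongest reply is that this hardly matters. Nothing is biased, no conclusion is invalidated, and power is already above 93%. Settling whether 540 or 603 subjects are analysed would move the interval more (1 − √(540/603) = 5.4%). With blocked strata the estimate itself becomes no more precise. All of that stands, and it limits the point to efficiency and consistency with the design.

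It can also be said that the size rests on inputs the documents do not give. That is right. The 0.5 to 2% range needs a roughly even split as well as a 1 to 2 lb gap; at 90/10 it falls to 0.2 to 0.7%. Equating the randomisation stratum with the survey item is likewise a reasonable reading, since section IV.C does not name its source.

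A third reply is that the plan already covers goal, through the known predictors in the protocol's mixed models and the baseline data in the imputation. This does not succeed. The first is not itemised and does not belong to the Analysis Plan's primary regression; the second concerns how missing values are filled in, not the model that estimates the effect.

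Finally, the Analysis Plan speaks of some follow-up events in the past tense, so altering the primary model is an amendment whose timing matters. That is fair and affects how the change is documented.

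**Conclusion.** The concern holds. Goal is the only stratification factor, and no outcome model in the Analysis Plan names it. For the linear one-year weight model the gain is about 0.5 to 2% in interval width, assuming a total SD of 5 lb, a 1 to 2 lb gap between strata and a split near even. It is smaller with an uneven split and nil with no gap. Power at 1.5 lb rises by less than one point in that range, and by about 0.1 to 0.5 points if strata were blocked. No narrowing applies to the logistic outcome, and no gain is claimed for Hypotheses 1.2, 2.1 or 2.2. The case for the change is that the analysis should follow the randomisation, that it costs almost nothing, and that it fixes which goal variable is meant.

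**What to change.** 1. Add the goal recorded at or before randomisation to the Hypothesis 1.1 regression and the weight mixed model: as a main effect where the outcome is a change score, as goal-by-time where it is the value at each visit.
2. For consistency with the design, add it to the models for Hypotheses 1.2, 2.1 and 2.2.
3. Define the variable by name and source. Exclude the calorie goal chosen in the intervention arm and any goal changed later.
4. Name the same variable in the multiple imputation model, so that it matches the outcome models.
5. For the binary outcome, state that the odds ratio is conditional on goal and the other covariates.
6. State whether randomisation was blocked within strata.
7. Date the change and record whether outcomes by arm had been seen. If they had, report the models with and without goal side by side.

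**Cost:** one covariate already collected at baseline, and about one degree of freedom in the change-score regression, or one more per follow-up visit with goal-by-time. No new data or subjects are needed. The conditional odds ratio will differ from the one without goal and its interval need not narrow; power did not fall in the settings simulated.
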